The risk to patients in this trial will be minimized by compliance with the eligibility criteria, close clinical monitoring and guidance for the investigators provided in the Investigator's Brochure. An adjudication committee will review cardiovascular events to confirm that these events have been evaluated appropriately and diagnosed correctly, while a Data Monitoring Committee (DMC) will monitor safety data from the study and the entire bimagrumab program for potential safety concerns.

As for any other investigational drug, there are unknown risks to bimagrumab, which may be serious and unforeseen.

Benefits

The benefits of bimagrumab treatment in the hip fracture population are still not known. However, it is expected that as seen in healthy volunteers and patients with sIBM, the hip fracture patients will have an increase in muscle mass that may translate to better recovery of lower extremity function and faster return to mobility. Over the course of the study, the number of falls might be reduced, which in turn reduces the risk of traumatic injuries and fractures, including secondary hip fractures.

4 Population

The study population will consist of male and female patients ≥ 60 years old, at time of randomization, who underwent surgical treatment for a low-energy fracture of the proximal femur. The study aims to screen approximately 400 patients. With an estimated screen failure rate of about 40%, approximately 245 patients, with successful surgery after hip fracture, will be randomized in more than 60 centers worldwide. Approximately 200 patients are expected to complete the 24-week treatment epoch and approximately 120 patients the full 48 -week study period.

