9.5 Analysis of secondary [REDACTED] variables

9.5.1 Efficacy variables

9.5.1.1 Gait speed and Short Physical Performance Battery (SPPB)

The change from baseline at Week 24 and Week 48 in gait speed and in SPPB will be analyzed similar to the primary variable. A log transformation may be used if warranted. An unstructured within subject correlation structure will be used for the covariance matrix.

In addition, dose response modeling will be performed for both gait speed and SPPB using the MCP-Mod approach.

The following testing strategy will be used to control for multiplicity of endpoints and doses to be tested: if both doses (210 and 700 mg) are statistically significantly different from placebo at $\alpha=0.05$ two-sided for the primary endpoint, then a fixed sequence approach will be applied for both Gait Speed and Short Physical Performance Battery (SPPB) at week 24 using the same linear mixed model for repeated measures and $\alpha=0.05$ two-sided at each stage. The first inference will compare the 700 mg group to placebo for Gait Speed, followed by a second inference comparing the 210 mg group to placebo for Gait Speed. The third inference will compare the 700 mg group to placebo for SPPB, followed by a fourth inference comparing the 210 mg group to placebo for SPPB. Additionally, the fifth inference will compare the combined 700 mg and 210 mg group to placebo for the incidence of fall observed till the time of the interim analysis. The analysis conducted at Week 24 for falls will include available incidence of falls also collected from patients with visits beyond Week 24. The analysis of the fall data will be performed based on the assumption that the differences in incidences of fall within the active bimagrumab doses (700 mg and 210 mg) is small compare to the differences of those doses to the placebo arm.

The sequence of the endpoints has been decided based on the anticipated probability of showing statistical significance of bimagrumab over placebo, the clinical importance is not considered for this sequence determination, as each endpoint is clinically important.

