9.7 Sample size and power calculation

A total sample size of approximately 245 patients at the time of randomization is planned (calculated using NQuery 7.0). Specifically, there will be 70 patients randomized to the placebo, bimagrumab 210 mg, and bimagrumab 700 mg groups for hypothesis testing purposes. An additional 35 patients will be randomized to the bimagrumab 70 mg group for the purpose of conducting formal dose response modeling described in the supportive analysis (section 9.4.4), but not for hypothesis testing. .

Total lean body mass

The primary objective of the study is to demonstrate that bimagrumab induces increases in Total LBM (change from baseline) compared to placebo at Week 24. A meaningful difference in LBM (change from baseline) increase has been identified as being 1.0 kg over placebo.

Study BYM338X2102 cohort 1&2 data showed that at Week 12, 5 subjects in 10 mg/kg bimagrumab group had LBM change from baseline mean = 1.48 kg (std = 0.86 kg); 6 subjects in 3 mg/kg bimagrumab group had LBM change from baseline mean = 2.22 kg (std = 1.13 kg).

Assuming that at Week 24 total LBM (change from baseline) difference between bimagrumab and placebo will be 1.0 kg and common SD = 1.0 kg, then sample size of 70 per group will show the power of 99%. Table 9-1 shows the power of detecting a significant difference between bimagrumab and placebo in LBM at Week 24 by two-sided test at alpha level = 0.025 (adjusted for 2 comparisons).

Table 9-1 Power calculation for total LBM (sample size = 70 per arm)

Common SD [kg]	Total LBM difference (bimagrumab – Placebo) [kg]				
	0.8	0.9	1.0	1.1	1.2
1.0	99	99	99	99	99
1.2	95	98	99	99	99
1.4	86	93	97	99	99
1.6	75	85	92	96	98

Gait Speed

One of the secondary objectives is to characterize for each bimagrumab treated group the placebo-corrected change in gait speed (GS) from baseline to Week 24. A treatment effect of 0.1-0.2 m/s between bimagrumab and Placebo has been deemed to be a clinically meaningful difference (Alley et al 2011).

The references in Table 9-2 were consulted in order to understand the variability and magnitude of treatment effect to be anticipated in 6 months on 4 m gait speed.

[figure not shown]

Table 9-2 Key references used to ascertain the variability in gait speed

Reference	Study Design	Population	Information

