The references in [Table 9-3](#) were consulted in order to understand the variability and magnitude of treatment effect to be anticipated on SPPB in 6 months. Common standard deviation for change from baseline at month 6 in SPPB have been estimated based on 95% confidence interval for the changes from baseline in SPPB from [Latham et al \(2014\)](#). When assuming respective group sample sizes of 95 and 100 and using a multiple imputation technique to address missing data, SD is estimated to 1.5. When assuming respective group sample sizes of 95 and 100 and using a multiple imputation technique to address missing data, SD is estimated to 1.4.

Table 9-3 Key references used to ascertain the variability in SPPB

Reference	Study Design	Population	Information
Latham et al (2008)	Randomized, double-blinded, placebo-controlled trial	Patients >65 years undergoing surgical repair of a hip fracture	SPPB at baseline 4.7 (2.8) SPPB at Week 12 7.9 (2.6)
Latham et al 2014	Randomized, double-blinded, placebo-controlled trial	232 functionally limited older (78-79 years) adults who had completed traditional rehabilitation after a hip fracture	SPPB at baseline 5.9 (2.8). SPPB at Week 24 6.2 (3.0) and 7.2 (3.0) in the placebo and exercise intervention groups, respectively Changes in SPPB from baseline at Month 6 was 0.2 (95% CI 0-0.5) in the control and 1.0 (95% CI 0.8-1.3) in the exercise group
Adunsky et al 2012	Randomized, double-blinded, placebo-controlled trial	123 patients 60+ years old with maximum 4 days after a non-complicated surgical hip fracture repair	SPPB at baseline was 9.1 (2.2) in the treated and 8.9 (2.6) in the placebo group, respectively Changes in SPPB from baseline were 4.5 (2.2) and 3.3 (2.7), respectively

Assuming that at Week 24 SPPB (change from baseline) difference between bimagrumab and placebo will be 1.0 point and common SD = 1.5 point, then sample size of 70 per group will give the power of 97% using a two-sided test at alpha level = 0.05 (based on testing strategy).

Falls

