A secondary objective of the study is to evaluate the effects of bimagrumab vs. placebo on the incidence of falls when the primary analysis is conducted. The analysis conducted for falls will include all available information collected in patients including information from visits after Week 24. Patients randomized to the active doses of 700mg and 210mg will be combined and compared to placebo, with the assumption that the differences in the incidences of fall within the bimagrumab doses (700 mg and 210mg) are minimal than the differences with the placebo arm. The annualized placebo fall rate is considered as 30% and a clinically meaningful ratio in the fall rate of the active doses relative to placebo is considered as 0.7 ([Gillespie et. al. \(2012\)](#)).

[Table 9-4](#) shows the power of detecting a significant difference between the active doses of bimagrumab and placebo in falls at Week 24, assuming sample sizes of 140 and 70 patients, respectively, negative binomial rates ([Zhu and Lakkis 2014](#)) with over dispersion parameter $k=1$ and using a two-sided test at alpha level = 0.05. It is also assumed that the average follow-up per patients will be 9 months.

[figure not shown]

Table 9-4 Power calculation for falls (sample size: BYM combined (210mg and 700mg) arm=140 and Placebo= 70)

Active bimagrumab annual fall rate	Placebo annual fall rate	Rate Ratio	Power, %
0.21	0.30	0.7	16.3
0.15	0.30	0.50	42.9
0.10	0.30	0.33	72.7
0.28	0.40	0.7	19.5
0.20	0.40	0.50	52.0

If the background placebo rate for the incidence of fall is 30% and if the rate reduction for the combined bimagrumab arm is 30% then the study will have less than 20% power. However, if the rate reduction is 67% (assuming the background placebo rate as 30%) then the study will have approximately 73% power.

10 Ethical considerations

[figure not shown]

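### The 97% (SPPB) and 73% (falls) powers are single-test figures; under the fixed sequence SPPB is declared in about 86–89% of trials and falls, in its most favourable row, in about 63–69%

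*Protocol*

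**What the plan says.** Protocol 9.5.1.1 opens secondary testing only "if both doses (210 and 700 mg) are statistically significantly different from placebo" on LBM. The tests then run in fixed order, each at two-sided 0.05: gait speed 700 mg, gait speed 210 mg, SPPB 700 mg, SPPB 210 mg, and falls for the two doses combined. On SPPB it reads: "The third inference will compare the 700 mg group to placebo for SPPB, followed by a fourth inference comparing the 210 mg group". SAP 2.10.2.3 repeats the sequence.

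Protocol 9.7 powers each endpoint separately. LBM uses a "two-sided test at alpha level = 0.025 (adjusted for 2 comparisons". Gait speed is given 94%. For SPPB, 70 per group "will give the power of 97% using a two-sided test at alpha level = 0.05 (based on testing strategy". The falls table runs from 16.3% to 72.7%, and the text adds that "if the rate reduction is 67% (assuming the background placebo rate as 30%) then the study will have approximately 73% power". SAP 2.13 carries the same figures and adds 92% for SPPB at 15% dropout (60 per group).

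Neither document gives the probability of reaching SPPB or falls, or a power for the sequence as a whole.

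**The concern.** A fixed sequence allows the full 0.05 at every step, and the price is that every earlier test must succeed. The power section uses the benefit but does not show the price. A reader who takes 97% as the chance of an SPPB claim would treat a missing claim as strong evidence against an effect. In part it may only mean that one gait-speed test failed and SPPB was never formally tested. The same holds for falls, which come last. SPPB and falls are both secondary objectives, and the data are meant to inform phase 3.

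**Working it through.** **Inputs from the plan.** Protocol 9.7: "there will be 70 patients randomized to the placebo, bimagrumab 210 mg, and bimagrumab 700 mg groups"; LBM "difference between bimagrumab and placebo will be 1.0 kg and common SD = 1.0 kg"; gait speed 0.15 m/sec, SD 0.25; SPPB 1.0 point, SD 1.5; falls 140 versus 70, dispersion k = 1, 9 months of follow-up (0.75 year).

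**Inputs not in the plan.** The correlations between endpoints are assumed. Gait–SPPB runs from 0 to 0.9. Falls–function (falls with gait speed and with SPPB) is 0 or 0.5.

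**Step 1: reproduce the printed powers.** For means, power = Φ(δ / (σ√(2/n)) − z), with z = 1.960 at 0.05 and 2.241 at 0.025.

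- LBM: 1.0 / √(2/70) = 5.916; 5.916 − 2.241 = 3.675, above 99.9% (printed 99%).
- Gait speed: 0.15 / (0.25√(2/70)) = 3.550; less 1.960 = 1.590, 94.4% (printed 94%).
- SPPB: 1.0 / (1.5√(2/70)) = 3.944; less 1.960 = 1.984, 97.6% (printed 97%).
- Falls, 0.10 versus 0.30 per year: SE² = (1/(0.75×0.10) + 1)/140 + (1/(0.75×0.30) + 1)/70 = 0.1024 + 0.0778 = 0.1802, SE 0.4245; ln 3 / 0.4245 = 2.588; less 1.960 = 0.628, 73.5% (printed 72.7%). The other four rows also agree within 1 point.

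The printed figures are therefore sound as single-comparison powers.

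**Step 2: the gates before SPPB.** The two doses share the placebo arm, so their test statistics correlate at 0.5 within an endpoint. Both LBM tests under Holm pass in 99.99%. Both gait-speed tests pass with probability Φ₂(1.590, 1.590; 0.5) = 90.2%. No later claim can exceed this, whatever the endpoint correlations.

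**Step 3: the full sequence.** Simulation of the joint normal test statistics, 70 per arm, with falls in the 72.7% row:

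| Gait–SPPB correlation | 0 | 0.5 | 0.8 | 0.9 |
|---|---|---|---|---|
| SPPB 700 mg declared | 88.1% | 88.8% | 89.6% | 89.9% |
| SPPB both doses declared | 86.3% | 87.5% | 88.9% | 89.6% |
| Falls, independent of function | 62.8% | 63.6% | 64.6% | 65.1% |
| Falls, falls–function correlation 0.5 | 67.3% | 67.6% | 68.2% | 68.5% |

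Using t in place of normal critical values lowers the SPPB figures by about half a point, hence about 88–89% and 86–89% for correlations 0 to 0.8. At rate ratio 0.7, falls moves from 16.3% to about 14% if independent of function and about 16% at correlation 0.5.

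**Step 4: the SAP's 15% dropout, 60 per arm.** Gait speed: 0.15 / (0.25√(2/60)) = 3.286; less 1.960 = 1.326, 90.8% per dose and 84.4% for both. The 2% printed for gait speed at this size in SAP 2.13 cannot be used. In sequence, SPPB 700 mg is about 80–83% and both doses about 77–82%.

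The SAP's 92% for SPPB alone does not reproduce at its stated alpha: 1.0 / (1.5√(2/60)) = 3.651; less 1.960 = 1.691, 95.5%. With z = 2.241 the result is 1.410, 92.1%, so the figure matches a 0.025 test.

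For falls at 120 versus 60, SE² = 14.333/120 + 5.444/60 = 0.2102, SE 0.4585, and stand-alone power is 66.9%. If falls are independent of function, the in-sequence figure is 0.669 × 0.776 = 52% to 0.669 × 0.822 = 55%.

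**The case against.** The strongest defence is that nothing has been miscalculated. Per-comparison power is a common way to report secondary endpoints, and Step 1 confirms the numbers. The reference to the testing strategy directly follows the alpha level. It can fairly be read as explaining why 0.05 is used here when LBM used 0.025, and the falls text does not carry it. That stands: this is a gap in labelling and reporting, not an arithmetic error. It does not answer the point that the sequence is specified and its effect on power is shown nowhere.

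Several stronger readings are tempting, and the documents do not support them.

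- A reader might infer that 65% is a ceiling for falls. It holds only if falls are independent of function, whereas Protocol 6.4.5 cites an association of gait speed with falls. Positive correlation raises the figure; the firm limit is the stand-alone 72.7%.
- A reader might combine the 60-per-arm SPPB gate with the 72.7% falls power. That mixes sample sizes, because 72.7% belongs to 140 versus 70.
- Protocol section 4 says "Approximately 200 patients are expected to complete the 24-week treatment epoch", and 70 × 200/245 = 57 per arm invites a still lower figure. That treats non-completers as contributing nothing. The mixed model uses all available data, SPPB is measured at every treatment visit, and patients who stop treatment return for end-of-treatment assessments.
- The low end of the SPPB range needs a gait–SPPB correlation near 0. Gait speed is an SPPB component, so the upper end is more plausible.

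The loss is also modest in places. SPPB stays above 80% at 70 per arm, and at rate ratio 0.7 the protocol already concedes less than 20% power for falls.

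**Conclusion.** The concern holds as a reporting defect that should be corrected. At the plan's effects and SDs with 70 per arm, the sequence delivers about 88–89% for SPPB 700 mg and 86–89% for both doses, where a reader sees 97%. At 60 per arm it delivers about 80–83% and 77–82%, where a reader sees 92%. Falls in the most favourable row is about 63–65% under independence and 67–69% at a falls–function correlation of 0.5, never above 72.7%. Nearly all the loss before SPPB arises at gait speed, where both doses must win; the LBM gate costs almost nothing at the planned SD.

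The 90% cap rests only on the plan's own gait-speed assumptions and the shared placebo arm. The figures below it also depend on the assumed correlations. Type I error control is not affected.

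**What to change.** In Protocol 9.7 and SAP 2.13, label the 97%, 92% and 73% as single-test powers, conditional on reaching that step. Beside each, print the probability of rejection within the full sequence at 70 and at 60 per arm, and state the endpoint correlations assumed. Compute the falls figures on one stated sample size throughout. While editing SAP 2.13, state the alpha behind the 92% and correct the 2% for gait speed, since the 60-per-arm chain depends on that step.

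The cost is a short simulation and restated text. Design, alpha and sample size do not change. The only downside is that the stated figures become less favourable.

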10.1 Regulatory and ethical compliance

This clinical study was designed and shall be implemented and reported in accordance with the ICH Harmonized Tripartite Guidelines for Good Clinical Practice, with applicable local regulations (including European Directive 2001/20/EC, US CFR 21, and Japanese Ministry of Health, Labor, and Welfare), and with the ethical principles laid down in the Declaration of Helsinki.

10.2 Informed consent procedures

Eligible patients may only be included in the study after providing written (witnessed, where required by law or regulation), IRB/IEC-approved informed consent, or, if incapable of doing so, after such consent has been provided by a legally acceptable representative of the patient. In cases where the patient's representative gives consent, the patient should be informed about the study to the extent possible given his/her understanding. If the patient is capable of doing so, he/she should indicate assent by personally signing and dating the written informed consent document or a separate assent form. Informed consent must be obtained before conducting any study-specific procedures (i.e. all of the procedures described in the protocol). The process of obtaining informed consent should be documented in the patient source documents.

Novartis will provide to investigators in a separate document a proposed informed consent form that complies with the ICH GCP guideline and regulatory requirements and is considered appropriate for this study. Any changes to the proposed consent form suggested by the investigator must be agreed to by Novartis before submission to the IRB/IEC, and a copy of the approved version must be provided to the Novartis monitor after IRB/IEC approval.

10.3 Responsibilities of the investigator and IRB/IEC

Before initiating a trial, the investigator/institution should obtain approval/favorable opinion from the Institutional Review Board/Independent Ethics Committee (IRB/IEC) for the trial protocol, written informed consent form(s), consent form updates, patient recruitment procedures (e.g., advertisements) and any other written information to be provided to patients. Prior to study start, the investigator is required to sign a protocol signature page confirming his/her agreement to conduct the study in accordance with these documents and all of the instructions and procedures found in this protocol and to give access to all relevant data and records to Novartis monitors, auditors, Novartis Clinical Quality Assurance representatives, designated agents of Novartis, IRBs/IECs, and regulatory authorities as required. If an inspection of the clinical site is requested by a regulatory authority, the investigator must inform Novartis immediately that this request has been made.

10.4 Publication of study protocol and results

Novartis assures that the key design elements of this protocol will be posted in a publicly accessible database such as clinicaltrials.gov. In addition, upon study completion and finalization of the study report the results of this trial will be either submitted for publication and/or posted in a publicly accessible database of clinical trial results.

[figure not shown]
11 Protocol adherence

This protocol defines the study objectives, the study procedures and the data to be collected on study participants. Additional assessments required to ensure safety of patients should be administered as deemed necessary on a case by case basis. Under no circumstances should an investigator collect additional data or conduct any additional procedures for any research related purpose involving any investigational drugs.

Investigators ascertain they will apply due diligence to avoid protocol deviations. If an investigator feels a protocol deviation would improve the conduct of the study this must be considered a protocol amendment, and unless such an amendment is agreed upon by Novartis and approved by the IRB/IEC it cannot be implemented. All significant protocol deviations will be recorded and reported in the clinical study report.


Zhu, H. and Lakkis, H. (2014) Sample size calculation for comparing two negative binomial rates. *Statist. Med.*, 33: 376-387. doi:10.1002/sim.5947

13 Appendix 1: Clinically notable laboratory values and vital signs

The following criteria will be used as guidance for notable abnormalities of key laboratory tests and vital signs.

Clinically notable values will be forwarded to Novartis at the same time that they are sent to the investigators. Any action based on these laboratory values should be discussed with Novartis personnel.

Table 13-1 Clinically Notable Lab Values and Vital Signs

[figure not shown]
Laboratory Variable	Notable Criteria
Lipase	≥3x ULN
Amylase	≥3x ULN
Hemoglobin	<8.0 g/dL
Glycated hemoglobin (HbA1c)	≥7.5%
Average blood glucose	≥9.0 mmol/L
Platelet count	<75000 mm ³
Estimated GFR*	<30 mL/min
Total bilirubin concentration	>1.5 x ULN
Total serum bilirubin	>1.6 mg/dL (27µmol/L)
AST	>3xULN
ALT	>3xULN
Vital Signs	
Systolic blood pressure	>180 mm Hg <90 mm Hg
Diastolic blood pressure	>100 mm Hg <50 mm Hg
Pulse	>100 bpm <60 bpm
ECG	
QTcF**	≥450 msec for males ≥460 msec for females

**Estimated Glomerular Filtration Rate using Modification of diet in Renal Disease (MDRD) equation*
***QT interval with Fridericia correction*

14 Appendix 2: Liver event and Laboratory trigger definitions and follow-up requirements

Table 14-1 Liver Event and Laboratory Trigger Definitions

Definition/ threshold

LIVER LABORATORY TRIGGERS	
 • $3 \times \text{ULN} < \text{ALT} / \text{AST} \leq 5 \times \text{ULN}$ • $1.5 \times \text{ULN} < \text{TBL} \leq 2 \times \text{ULN}$
LIVER EVENTS	
 • $\text{ALT or AST} > 5 \times \text{ULN}$ • $\text{ALP} > 2 \times \text{ULN}$ (in the absence of known bone pathology) • $\text{TBL} > 2 \times \text{ULN}$ (in the absence of known Gilbert syndrome) • $\text{ALT or AST} > 3 \times \text{ULN}$ and $\text{INR} > 1.5$ • Potential Hy's Law cases (defined as $\text{ALT or AST} > 3 \times \text{ULN}$ and $\text{TBL} > 2 \times \text{ULN}$ [mainly conjugated fraction] without notable increase in ALP to $> 2 \times \text{ULN}$) • Any clinical event of jaundice (or equivalent term) • $\text{ALT or AST} > 3 \times \text{ULN}$ accompanied by (general) malaise, fatigue, abdominal pain, nausea, or vomiting, or rash with eosinophilia • Any adverse event potentially indicative of a liver toxicity *

*These events cover the following: hepatic failure, fibrosis and cirrhosis, and other liver damage-related conditions; the non-infectious hepatitis; the benign, malignant and unspecified liver neoplasms.

Table 14-2 Follow Up Requirements for Liver Events and Laboratory Triggers

Criteria	Actions required	Follow-up monitoring
Potential Hy's Law case ^a	
 • Discontinue the study drug immediately • Hospitalize, if clinically appropriate • Establish causality • Complete liver CRF 	ALT, AST, TBL, Alb, PT/INR, ALP and γ GT until resolution ^c (frequency at investigator discretion)
ALT or AST		
$> 8 \times \text{ULN}$	
 • Discontinue the study drug immediately • Repeat LFT within 48 hours • Hospitalize if clinically appropriate • Establish causality • Complete liver CRF 	ALT, AST, TBL, Alb, PT/INR, ALP and γ GT until resolution ^c (frequency at investigator discretion)
$> 3 \times \text{ULN}$ and $\text{INR} > 1.5$	
 • Discontinue the study drug immediately • Hospitalize, if clinically appropriate • Establish causality • Complete liver CRF 	ALT, AST, TBL, Alb, PT/INR, ALP and γ GT until resolution ^c (frequency at investigator discretion)
> 5 to $\leq 8 \times \text{ULN}$	
 • Repeat LFT within 48 hours • If elevation persists, continue follow-up monitoring • If elevation persists for more than 2 weeks, discontinue the study drug 	ALT, AST, TBL, Alb, PT/INR, ALP and γ GT until resolution ^c (frequency at investigator discretion)

Criteria	Actions required	Follow-up monitoring
	
 Establish causality Complete liver CRF 	
> 3 × ULN accompanied by symptoms ^b	
 Discontinue the study drug immediately Hospitalize if clinically appropriate Establish causality Complete liver CRF 	ALT, AST, TBL, Alb, PT/INR, ALP and γGT until resolution ^c (frequency at investigator discretion)
> 3 to ≤ 5 × ULN (patient is asymptomatic)	
 Repeat LFT within the next week If elevation is confirmed, initiate close observation of the patient 	Investigator discretion Monitor LFT within 1 to 4 weeks
ALP (isolated)		
> 2 × ULN (in the absence of known bone pathology)	
 Repeat LFT within 48 hours If elevation persists, establish causality Complete liver CRF 	Investigator discretion Monitor LFT within 1 to 4 weeks or at next visit
TBL (isolated)		
> 2 × ULN (in the absence of known Gilbert syndrome)	
 Repeat LFT within 48 hours If elevation persists, discontinue the study drug immediately Hospitalize if clinically appropriate Establish causality Complete liver CRF 	ALT, AST, TBL, Alb, PT/INR, ALP and γGT until resolution ^c (frequency at investigator discretion) Test for hemolysis (e.g., reticulocytes, haptoglobin, unconjugated [indirect] bilirubin)
> 1.5 to ≤ 2 × ULN (patient is asymptomatic)	
 Repeat LFT within the next week If elevation is confirmed, initiate close observation of the patient 	Investigator discretion Monitor LFT within 1 to 4 weeks or at next visit
Jaundice	
 Discontinue the study drug immediately Hospitalize the patient Establish causality Complete liver CRF 	ALT, AST, TBL, Alb, PT/INR, ALP and γGT until resolution ^c (frequency at investigator discretion)
Any AE potentially indicative of a liver toxicity*	
 Consider study drug interruption or discontinuation Hospitalization if clinically appropriate Establish causality Complete liver CRF 	Investigator discretion

*These events cover the following: hepatic failure, fibrosis and cirrhosis, and other liver damage-related conditions; the non-infectious hepatitis; the benign, malignant and unspecified liver neoplasms

^aElevated ALT/AST > 3 × ULN and TBL > 2 × ULN but without notable increase in ALP to > 2 × ULN

^b(General) malaise, fatigue, abdominal pain, nausea, or vomiting, or rash with eosinophilia

^cResolution is defined as an outcome of one of the following: (1) return to baseline values, (2)

Criteria	Actions required	Follow-up monitoring
		stable values at three subsequent monitoring visits at least 2 weeks apart, (3) remain at elevated level after a maximum of 6 months, (4) liver transplantation, and (5) death.
